#### **Risk window for all outcomes except Malignancy excluding NMSC and NMSC**

The risk window will be from the *index date* until *end of follow-up* for the ITT exposure definition, while for the time-varying exposure definition, where the exposure status may change over time, the risk window will depend on exposure status as illustrated in [Figure 1](#), including also non-exposed time.

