## 9. Research Methods

### 9.1. Study Design

The study is based on data from the nationwide health and administrative registers from Denmark and Sweden, covering country populations of approximately 5.8 million and 10.2 million people, respectively. It is a longitudinal, non-interventional, population-based, register-based cohort study of adolescents and adults with AD exposed to upadacitinib or other select systemic AD treatments, identified in the Danish and Swedish nationwide registers.

Importantly, labelling changes following Article 20 procedure are likely to result in substantial differences in baseline characteristics of patients initiating upadacitinib and those initiating other systemic treatments. Therefore, initial in-depth descriptive analyses will be conducted to assess comparability across treatment cohorts and inform the design (including selection of suitable comparator/s) of subsequent analyses.

The select systemic AD treatments (including biosimilars) evaluated as potential comparator treatments in the study are:

- Azathioprine
- Ciclosporin
- Dupilumab
- Methotrexate
- Mycophenolate mofetil

ATC codes and procedure codes for the comparator treatments are listed in Annex 3. Additional Information, [Table 3.2](#). Additional upcoming marketed AD treatments may become relevant as comparator treatments as the study progresses. Therefore, the list may be extended to cover

other available and approved AD treatments in Sweden and Denmark during the study period. Final codes and definitions will be specified in the Statistical Analysis Plan (SAP) before data extraction for interim analysis and final analysis.

A *new user*, active comparator design will be used to address the objectives of the study. *New user* is defined as not having used that specific drug substance in the year (12 months, 365 days) before the first eligible treatment.

The first dispensed prescription/administration date of upadacitinib or one of the comparator treatments within the study period (see definition in Section 9.2.2. ), will be defined as the *index date*.

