### 9.2.3. Follow-Up

Each individual will be followed specifically for each outcome of interest, from the *index date* to the earliest occurrence of the specific outcome of interest, end of the study period, emigration, death or initiation of any other JAK inhibitor.

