#### 9.4. Data Sources

Data from the national patient registers, the national prescribed drug registers, the national cancer registers, the cause of death registers and the population-based registers in Denmark and Sweden will be used. In addition, the Danish Hospital Medicines Register (if available at the time of data extraction) and the Danish Educational and Socioeconomic Registries will be used.

The assignment of unique personal identification numbers (PIN) to all Danish and Swedish residents at birth or upon immigration makes it possible to cross-link data between the national registers within each country. The PIN is kept unchanged throughout life, so individuals can be followed-up throughout their lifetime, except for migrants. The registers are updated on a yearly basis with up to two years production time before released to research, depending on content. The registers contain the following information:

- From the population-based registers and the Danish Educational and Socioeconomic Registries information on demographic variables, migration and socioeconomic factors will be obtained.
- The national patient registers contain information on all hospitalizations and outpatient visits to specialist care, including primary and secondary diagnoses recorded at discharge. Diagnoses of AD, medical history, comorbidities, and outcomes are recorded according to the International Classification of Diseases, revision 10 (ICD-10).
- The national cancer registers contain information on all incident cancer diagnoses (morphologically verified). In addition, information about cancer diagnoses might also be obtained from the national patient registers.
- The date and cause of death will be obtained from the cause of death registers. In Denmark civil registration system will be used for identifying date of death.

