- The prescribed drug registers include data on the formulations and date of all dispensed prescriptions. Drugs are categorized according to the WHO Anatomical Therapeutic Chemical classification system (ATC codes) [20]. Main exposure in Sweden will be defined based on dispensed prescriptions from the prescribed drug register for all treatments, while in Denmark exposure will be captured by treatment codes in the patient register and dispensed prescriptions in the prescribed drug register. When captured by treatment codes in the patient register information about dose, strength, amount dispensed will not be available. If available, Danish Hospital Medicines Registry might be used in addition. This data source is currently undergoing testing and may become available in 2023.
- The contagious disease register, since 1971, provides events reported according to the Swedish Communicable Diseases Act and the communicable diseases ordinance on diseases e.g. TB that have mandatory reporting in Sweden.

The above-mentioned national registers hold data on almost all inhabitants in Sweden (population 10.2 million) and Denmark (population 5.8 million). The coverage and quality of the Danish and Swedish Registers have been well established in the literature [21]. Due to the breadth of capture of clinical outcomes across providers as well as “cradle to grave” longitudinal coverage, these registries have been successfully utilized for numerous post-marketing safety studies.

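### The risk window for non-malignancy outcomes opens on the index date itself, so a condition already present at a Danish hospital contact where treatment began can be counted as a post-exposure event

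*Protocol*

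**What the plan says.** Section 9.2.3 follows each individual "from the *index date* to the earliest occurrence of the specific outcome of interest" or a censoring event. Section 9.3.2 repeats this start for all outcomes except malignancy and NMSC: "The risk window will be from the *index date* until *end of follow-up* for the ITT exposure definition".

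Section 9.1 defines the index date: "The first dispensed prescription/administration date of upadacitinib or one of the comparator treatments within the study period". Section 9.4 says where those dates come from. For Sweden: "Main exposure in Sweden will be defined based on dispensed prescriptions from the prescribed drug register for all treatments". For Denmark, "in Denmark exposure will be captured by treatment codes in the patient register and dispensed prescriptions in the prescribed drug register".

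Under section 9.3.2 the non-malignancy outcomes come from inpatient and specialist outpatient diagnoses in the national patient registers. Section 9.4 describes the content of those registers, "including primary and secondary diagnoses recorded at discharge". Table 3.3 lists history look-backs of 1 or 5 years for most outcomes.

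Malignancy and NMSC are handled differently. Their window opens after a 12-month lag, and events within the lag become medical history.

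**The concern.** When the index record is a Danish treatment code, it belongs to a hospital contact, and that contact also generates diagnoses in the register used for outcomes. No rule separates a condition that was present when the drug was started from one that followed it. The look-back removes people with an earlier record of the outcome. It does not clearly remove a first diagnosis dated on day 0.

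The protocol's own background makes the overlap plausible. Section 7 notes that bacterial infection can trigger exacerbations of atopic dermatitis, and that eczema herpeticum may require admission. Either can share a contact with the start of a systemic drug.

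Two results are at stake. The first is the crude incidence of each outcome in upadacitinib users, a primary objective. The second is the hazard ratio against a comparator, if one is found suitable. Unequal capture of the comparator by treatment code would make upadacitinib look safer than it is, which is the wrong direction of error for a safety study.

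**Working it through.** **No figure to reproduce.** The protocol gives no number on this point and section 9.5 is redacted. The check sets the rules side by side and then illustrates the size.

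**Which day-0 diagnoses fall inside the window**

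- *Outpatient contact on one day.* Start and end coincide, so a diagnosis from that contact is dated on the index date and falls inside the window.
- *Admission with the drug started on the first day.* Dated at admission or at discharge, the diagnosis falls on or after the index date, so inside.
- *Admission with the drug started later in the stay.* Dated at admission, the diagnosis precedes the index date and is history. Dated at discharge, it is inside. The protocol does not say which date applies; diagnoses being recorded at discharge does not settle how an event is dated.
- *Pharmacy dispensing.* The record carries no diagnosis, but it can fall on the day of a specialist visit, whose diagnosis would then also be inside.

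So a treatment-code start always sits in a hospital contact, while a dispensing need not. The difference between the two routes is one of degree.

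**Which outcomes are exposed.** Malignancy and NMSC are protected by the lag in the main analysis; only the 0-month sensitivity analysis is open to the problem. Serious infections are defined as in-patient, so a purely outpatient start cannot produce one at that contact. The other diagnosis-based outcomes admit specialist outpatient diagnoses.

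**Size.** Let r be the true event rate per 1,000 person-years, T the mean years at risk, and q the spurious day-0 events per 1,000 initiators. The crude rate in an affected cohort becomes r + q/T. If only the comparator is affected and the true hazard ratio is 1, the observed ratio is approximately

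HR = r / (r + q/T).

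All inputs below are assumptions; the documents give none of them.

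| r | T | q | Calculation | Observed HR |
|---|---|---|---|---|
| 20 | 5 | 0.1 | 20/20.02 | 0.999 |
| 5 | 5 | 1 | 5/5.2 | 0.96 |
| 5 | 2 | 1 | 5/5.5 | 0.91 |
| 5 | 1 | 1 | 5/6 | 0.83 |
| 2 | 2 | 5 | 2/4.5 | 0.444 |

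The same arithmetic gives the inflation of crude incidence in any affected cohort: 0.2/5 = 4% in the second row and 2.5/2 = 125% in the last.

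**Dependence on follow-up.** Assume r = 10, half of Danish comparator starts captured by treatment code, and 1% of those with an outcome code at the index contact. Then 1,000 × 0.5 × 0.01 = 5 events are added per 1,000 Danish starters. Assume also that Denmark contributes to the pooled cohort in proportion to population, 5.8/(5.8 + 10.2) = 0.3625. The pooled addition is then 5 × 0.3625 = 1.81.

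- T = 1: 10 expected. Denmark +50%, HR 1/1.5 = 0.67. Pooled +18%, HR 0.85.
- T = 5: 50 expected. Denmark +10%, HR 50/55 = 0.91. Pooled +3.6%, HR about 0.97.

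The added events are fixed at the start of follow-up, so long ITT follow-up dilutes them and short on-treatment time does not.

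**The case against.** The strongest reply is that the day-0 convention and event dating are ordinary SAP matters, and that section 9.1 and Annex 3 defer final codes and definitions to the SAP. This stands for event dating. It does not stand for the start of the window, which sections 9.2.3 and 9.3.2 fix in words and do not defer.

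Three stronger readings are tempting, and the documents do not support them.

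- *That diagnoses from the index contact always count as events.* For an admission that began before the drug was given, this depends on a dating rule the protocol does not state.
- *That only comparators are captured by treatment code.* Section 9.1 points that way: "ATC codes and procedure codes for the comparator treatments are listed in Annex 3". But section 9.4 describes Danish capture for exposure in general, and the codes in Table 3.2 are redacted. Counting redaction bars is weak evidence, and on that count methotrexate would have no procedure code either. No comparator has been fixed.
- *That a hazard ratio of 0.67 or 0.85 is to be expected.* Those figures need one year at risk and capture and coding proportions without a source. ITT follow-up can run to December 2031, and section 9.7.2 plans a pooled analysis unless legal barriers prevent it.

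A simple remedy can also do harm. Starting follow-up after discharge only for hospital-coded drugs would make time zero differ by capture route. Dropping deaths in the index stay would remove cardiovascular deaths from MACE while all-cause mortality kept them.

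**Conclusion.** The point holds as a defect in a stated rule. The window includes the index date, and in Denmark that date can belong to a hospital contact in the register that supplies the outcomes. Conditions already present at that contact can therefore be counted as post-exposure events, and crude incidence can be inflated in any cohort captured this way, upadacitinib included.

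The effect on the hazard ratio depends on how capture differs between cohorts. If comparators are captured by treatment code more often, the ratio for upadacitinib is biased downwards. If capture is similar, adding the same amount to both rates pulls the ratio towards 1. The first case is suggested by section 9.1 but not confirmed.

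The size cannot be determined from the documents. Under the assumed inputs it runs from negligible (0.999) to material (0.444). It is small for common outcomes over long ITT follow-up, and largest for rare acute outcomes or short on-treatment time. The problem is confined to Danish initiators whose index record is a treatment code, apart from the lesser same-day-visit overlap, which can occur in either country. It deserves correction because the remedy is cheap and the likely direction of error is unfavourable; a shift in the results has not been shown.

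**What to change.** In sections 9.2.3 and 9.3.2:

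1. Start the risk window for non-fatal, non-malignancy outcomes on the day after the index date, for every cohort and in both countries. Time zero is then the same whatever the capture route.
2. Treat diagnoses dated on the index date, or belonging to the hospital contact that contains it, as history subject to the Table 3.3 look-back. No look-back is visible there for MACE, so say what happens to a person with an infarction or stroke at the index contact.
3. State whether events are dated at admission or at discharge.
4. Keep deaths counted from the index date, both all-cause mortality and the cardiovascular death component of MACE. A death cannot have been present before treatment began.
5. Add a sensitivity analysis that includes day 0 and index-contact diagnoses.

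The cost is a few sentences and a small programming change. At most one day is lost from a study period of 3,783 days (23 August 2021 to 31 December 2031, both included). A few true events on day 0 or during the index contact will be lost, and for people treated during an admission the rest of that stay becomes person-time in which only deaths can count. The sensitivity analysis shows how much this matters.

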#### **Risk window for Malignancy excluding NMSC and NMSC outcomes**

The risk window will start from a lag-time of 12 months after *index date* until the *end of follow-up* for the ITT and modified ITT exposure definitions. Events occurring during the lag-time will not be counted, instead they will be counted as medical history. Similarly, the follow-up included in the lag-time will be disregarded. Sensitivity analyses with 0- and 6-months lag time will be conducted.

### **9.3.3. Baseline Variables**

In addition to exposures and outcomes, other variables that are recorded in the national registers will be included in this study. These variables will include demographic and socioeconomic measures (e.g., age, sex, region of residency, education, income, occupation, country of origin), proxy measures for lifestyle factors (e.g., smoking, alcohol use), comorbidities, past and present medication use, and prior medical procedures. As a proxy measure of disease severity, healthcare utilization within one year before cohort entry will be studied.

A list of baseline variables is presented in [Table 1](#). In general, one-year look-back period prior to *index date* will be used for medication use and disease severity proxies and five years for all the other variables.

**Table 1 Baseline Variables**

Data type	Description
Demographics and socioeconomics	Age Sex Education Income Occupation Region of residency
Lifestyle factors	Smoking (identified through proxies) Alcohol use (identified through proxies)
Medical history within 5 years prior to index date	Asthma Obesity Hypertension Hyperlipidemia Diabetes Myocardial infarction Stroke Peripheral vascular disease Rheumatoid arthritis Depression Anxiety Insomnia Chronic obstructive pulmonary disease (COPD) Moderate hepatic impairment Serious infection Active TB Atherosclerotic cardiovascular disease Malignancy Chronic infection with hepatitis B virus (HBV) or hepatitis C virus (HCV) Severe renal impairment Endogenous uveitis Nephrotic syndrome Transplantation (organ/bone marrow) Psoriasis Crohn's disease Ulcerative colitis Celiac disease Acute lymphocytic leukemia (ALL) Systemic lupus erythematosus (SLE) Polymyositis and dermatomyositis Pemphigus Polyarteritis nodosa Autoimmune hemolytic anemia Chronic Idiopathic (Immune) Thrombocytopenic Purpura Polyarticular Severe Active Juvenile Idiopathic Arthritis External Otitis Previous fracture
Medication use within 1 year prior to index date	Antihypertensives Lipid-lowering drugs Antidepressants Anxiolytic drugs Antipsychotics Insomnia medications

Use of AD treatments other than the ones being studied within 1 year prior to index date	Biologic Non-biologic systemics Phototherapy Topical agents
Healthcare utilization as proxies of AD severity within 1 year prior to index date	Number of AD inpatient days at baseline Number of AD outpatient visits at baseline Number of non-AD inpatient days at baseline Number of non-AD outpatient visits at baseline

#### 9.4. Data Sources

Data from the national patient registers, the national prescribed drug registers, the national cancer registers, the cause of death registers and the population-based registers in Denmark and Sweden will be used. In addition, the Danish Hospital Medicines Register (if available at the time of data extraction) and the Danish Educational and Socioeconomic Registries will be used.

The assignment of unique personal identification numbers (PIN) to all Danish and Swedish residents at birth or upon immigration makes it possible to cross-link data between the national registers within each country. The PIN is kept unchanged throughout life, so individuals can be followed-up throughout their lifetime, except for migrants. The registers are updated on a yearly basis with up to two years production time before released to research, depending on content. The registers contain the following information:

- From the population-based registers and the Danish Educational and Socioeconomic Registries information on demographic variables, migration and socioeconomic factors will be obtained.
- The national patient registers contain information on all hospitalizations and outpatient visits to specialist care, including primary and secondary diagnoses recorded at discharge. Diagnoses of AD, medical history, comorbidities, and outcomes are recorded according to the International Classification of Diseases, revision 10 (ICD-10).
- The national cancer registers contain information on all incident cancer diagnoses (morphologically verified). In addition, information about cancer diagnoses might also be obtained from the national patient registers.
- The date and cause of death will be obtained from the cause of death registers. In Denmark civil registration system will be used for identifying date of death.
- The prescribed drug registers include data on the formulations and date of all dispensed prescriptions. Drugs are categorized according to the WHO Anatomical Therapeutic Chemical classification system (ATC codes) [20]. Main exposure in Sweden will be defined based on dispensed prescriptions from the prescribed drug register for all treatments, while in Denmark exposure will be captured by treatment codes in the patient register and dispensed prescriptions in the prescribed drug register. When captured by treatment codes in the patient register information about dose, strength, amount dispensed will not be available. If available, Danish Hospital Medicines Registry might be used in addition. This data source is currently undergoing testing and may become available in 2023.
- The contagious disease register, since 1971, provides events reported according to the Swedish Communicable Diseases Act and the communicable diseases ordinance on diseases e.g. TB that have mandatory reporting in Sweden.

The above-mentioned national registers hold data on almost all inhabitants in Sweden (population 10.2 million) and Denmark (population 5.8 million). The coverage and quality of the Danish and Swedish Registers have been well established in the literature [21]. Due to the breadth of capture of clinical outcomes across providers as well as “cradle to grave” longitudinal coverage, these registries have been successfully utilized for numerous post-marketing safety studies.

**Table 2 Data Sources in Denmark and Sweden**

[figure not shown]
Sweden	Denmark
[REDACTED]	[REDACTED]
[REDACTED]	[REDACTED]
[REDACTED]	[REDACTED]
[REDACTED]	[REDACTED]
[REDACTED]	[REDACTED]
[REDACTED]	[REDACTED]
[REDACTED]	[REDACTED]
[REDACTED]	[REDACTED]

[figure not shown]
**9.5. Study Size**

[figure not shown]
[REDACTED]

[figure not shown]
- [REDACTED]
- [REDACTED]
- [REDACTED]
- [REDACTED]
- [REDACTED]

[REDACTED]

Since the potential available number of patients exposed to upadacitinib and comparators in the first five accrual years in the national registers in Denmark and Sweden is higher than the required target number of patients for the estimated sample size for the most important outcomes, these data sources are considered sufficient for this study.

The number of patients exposed to upadacitinib and other select systemic AD treatments will be monitored annually. If the number of upadacitinib users does not reach 50% of the target sample size by year 2024 (captured in the progress report in 2026), additional data sources will be considered to be added to the study.

### **9.6. Data Management**

Data retrieval and management will be conducted separately in each country. The coordinating investigator in each country will obtain all necessary permissions and prepare a data application to its country-specific data custodian. The data holders in each country will create a unique dummy study identification number (SID) for each PIN. The coordinating investigator in each country will then receive the data where the PINs have been replaced by SIDs and these will be used for data linkage at the patient level. Therefore, the coordinating investigators in each country have access to pseudonymized data only.

In Sweden, data from the Swedish health registers will be provided by the Swedish National Board of Health and Welfare. Population data and socioeconomic data will be provided by Statistics Sweden. The pseudonymized individual-level data will be stored at a secure server at KI, and only members of the research team will have access to the data.

In Denmark, pseudonymized data from the Danish population, education, and health registers will be provided by Statistics Denmark. The register data will be accessed on-line via a password protected safe data portal.

Data will be cleaned and coded and harmonized analytic datasets will be prepared according to the specifications provided in the SAP. A full audit trail, starting from raw data obtained from register holders and ending with the creation of statistical tables and graphs in reports, will be maintained. For cross-country pooled analyses, pseudonymized external data from the Swedish national health and population registers, will be provided by KI and uploaded at the safe data portal at Statistics Denmark, and members of the Swedish research team will have access to the data. Legal barriers towards transfer of individual data might be an issue, and if so meta-analyses of aggregated data will be performed instead of cross-country pooled analyses.

The statistical software packages STATA, R, and SAS will be used for data management and analyses.

